THE STUDY PROTOCOL

date: 2024-07-16

PROTOCOL ID: UMED-RNN/223/20/KE

Title: Evaluation of the Effectiveness and Safety of Blue Light Emitted by LED Lamps Using the PHLECS Device in the Treatment of Inflammatory Skin Diseases

THE STUDY PROTOCOL

date: 2024-07-16

ID: UMED-RNN/223/20/KE

Title: Evaluation of the Effectiveness and Safety of Blue Light Emitted by LED Lamps Using the PHLECS Device in the Treatment of Inflammatory Skin Diseases

- The study involves four groups of patients (patients with psoriasis, atopic dermatitis, eczema and chronic pruritus)
- The study is scheduled for a maximum of 60 irradiations of blue light (maximum 3 cycles of 20 irradiations each). Phototherapeutic light will be administered for 15 minutes to each side of the body of the patient (30 minutes in total), 3-5 times per week.
- Device

Full Body Blue GEN 1.0 device (built by PHLECS B.V., Phlecs, [name]) with European Community (EC) Certificate (number 2238613CE01) is used in the study. The device provides phototherapeutic light through light panel with treatment Light Emitting Diodes - LEDs (wavelength 453 nm, irradiance 40mW/cm²; dose 36J for 15min treatment) to one side of the body of the patient who is lying flat on an examination bed

- After consent to participate in this study, the observation period will begin and will last a maximum of 12 weeks

1. Day 0 - screening and inclusion, during which the following will be assessed:

- skin examination (including photo documentation), assessing skin phototype according to Fitzpatrick's scale
- detailed medical history collection
- quality of life assessment – DLQI
- Additionally, appropriate scales will be used depending on the disease:
PASI, PGA, VAS, 10-item Pruritus Severity Scale - psoriasis vulgaris
IGA, VAS, 10-item Pruritus Severity Scale - eczema
SCORAD, EASI, VAS, 10-item Pruritus Severity Scale - atopic dermatitis
VAS, 10-item Pruritus Severity Scale – chronic pruritus
- an interview will be made regarding comorbidities and the treatment used
- blood samples collection
- Optionally, only in patients who give additional consent a skin biopsy will be taken to evaluate the mechanism of action of blue light.

2. visit 1 – first full-body blue irradiation

3. Visit 2 – evaluation of the effectiveness and safety after 10 sessions of blue light phototherapy, Blood sample collection
4. Visit 3 – evaluation of the effectiveness and safety after 20 sessions of blue light phototherapy (= after the first cycle of irradiation), Blood sample collection
5. Visit 4 – evaluation of the effectiveness and safety after 30 sessions of blue light phototherapy, Blood sample collection
6. Visit 5 – evaluation of the effectiveness and safety after 40 sessions of blue light phototherapy (= after the second cycle of irradiation), Blood sample collection
7. Visit 6 – evaluation of the effectiveness and safety after 50 sessions of blue light phototherapy, Blood sample collection
8. Visit 7 - end of treatment visit - after 60 sessions of blue light phototherapy (= after the third radiation cycle), during which we will re-evaluate the condition of the skin, quality of life, safety of the device used and blood samples will be taken. Optionally, with additional consent, a skin biopsy will be taken. If, for any reason, the study is terminated earlier or if the skin lesions have completely disappeared before 60 irradiations - the end of treatment visit will take place earlier
9. Visit 8 – assessment of the clinical condition 4 weeks after the cessation of therapy

During blue light therapy, follow-up visits will be performed to assess the safety and effectiveness of the device. At the last control visit (end of treatment visit) the same parameters will be assessed as during the first one. In the case of remission of skin lesions earlier than envisaged in the study protocol, the end of treatment visit will take place earlier. Photographic documentation will be carried out at each visit. During the treatment patients were allowed to use emollients.

Inclusion criteria:

1. Informed consent to participate in a medical experiment
2. Age over 8 years of age
3. Diagnosis of psoriasis / eczema / atopic dermatitis
4. Chronic pruritus (lasting more than 6 weeks)
5. Good general health (no history of other clinically significant diseases according to the doctor's assessment)
6. A patient who is able to understand the information related to the experiment, meet the requirements contained in the protocol of the experiment, who undertakes to strictly follow medical recommendations and appear on time for visits.

Exclusion criteria:

1. Patients with known hypersensitivity to ultraviolet or blue radiation
2. Age under 8 years of age
3. Women who are pregnant, breastfeeding or planning to become pregnant during the experiment
4. Patients who participated in another experiment / clinical trial within 30 days prior to inclusion in the experiment
5. Patients unwilling or unable to respect the requirements of the experiment
6. Patients with skin diseases other than inflammatory skin diseases or chronic pruritus
7. Planned hospitalizations or surgical procedures during the medical experiment
8. Patients using medications with proven phototoxic effect
9. Diastolic blood pressure > 95mmHg and < 65mmHg
10. Patients with congenital or acquired immune disorders

11. Patients with a history or at the time of the examination diagnosed with a malignant skin cancer, severe actinic keratosis or dysplastic moles
12. Patients diagnosed with genophotodermatoses, increasing the risk of skin cancers, including xeroderma pigmentosum, Cockayne's syndrome, Bloom's syndrome)
13. Patients addicted to alcohol / drugs in the last 12 months

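### The 12-week maximum observation period cannot hold the protocol's own full schedule: 60 sessions at 3 to 5 per week plus Visit 8 take 16 to 24 weeks

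*Protocol*

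**What the plan says.** Four statements in the protocol bear on how long a patient is in the study.

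- **Opening bullet list, observation period.** Once consent is given, "the observation period will begin and will last a maximum of 12 weeks". The clock starts at consent, not at the first irradiation.
- **Opening bullet list, number and frequency of sessions.** "The study is scheduled for a maximum of 60 irradiations of blue light (maximum 3 cycles of 20 irradiations each"), at a rate given as "30 minutes in total), 3-5 times per week".
- **Visit schedule, items 3 to 8.** Visits 2 to 7 are triggered by session count, every 10 sessions from 10 to 60. The last of these is "Visit 7 - end of treatment visit - after 60 sessions of blue light phototherapy (= after the third radiation cycle"). The same item allows this visit to come sooner: "If, for any reason, the study is terminated earlier or if the skin lesions have completely disappeared before 60 irradiations".
- **Visit schedule, item 9.** "Visit 8 – assessment of the clinical condition 4 weeks after the cessation of therapy".

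The paragraph after the visit schedule adds: "At the last control visit (end of treatment visit) the same parameters will be assessed as during the first one". This treats the end-of-treatment visit, not Visit 8, as the last control visit.

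No passage defines the observation period as treatment only, excludes Visit 8 from it, or names week 12 as a reason to stop treatment.

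**The concern.** A stated maximum duration should cover the longest course that the same document permits. Here the maximum number of sessions, the range of frequencies and the timing of Visit 8 together fix how long a full course lasts, and the result does not appear to fit into 12 weeks.

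What is at stake depends on how the 12 weeks are applied.

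- **Applied as a cut-off.** Because Visits 2 to 7 depend on session count, attendance frequency would decide which late assessments a patient has. Patients treated less often would not reach the later ones. Their end-of-treatment visit would still take place, but before 60 sessions, and Visit 8 would usually fall outside the period.
- **Not applied.** The stated maximum is wrong for anyone who receives a full course, and those running the study have no stated maximum that covers it.

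**Working it through.** **Inputs, all from the protocol**

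- Maximum observation period from consent: 12 weeks (opening bullets).
- Maximum sessions: 60, in 3 cycles of 20 (opening bullets).
- Frequency: 3 to 5 per week (opening bullets).
- Visit 8: 4 weeks after treatment stops (visit schedule, item 9).

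**Step 1. Can the 12 weeks be reproduced?** Only in one way: 60 / 5 = 12 weeks. That is treatment alone at the highest permitted frequency, with no missed session, no gap between consent and the first session, and no Visit 8.

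**Step 2. Length of a full course.** Treatment weeks = 60 / sessions per week. Total = treatment weeks + 4.

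| Sessions per week | Treatment (weeks) | Through Visit 8 (weeks) | Excess over 12, treatment only | Excess over 12, through Visit 8 |
|---|---|---|---|---|
| 5 | 60/5 = 12 | 16 | 0 | 4 |
| 4 | 60/4 = 15 | 19 | 3 | 7 |
| 3 | 60/3 = 20 | 24 | 8 | 12 |

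Any gap between consent and Visit 1 adds to these figures.

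**Step 3. What fits if week 12 is a cut-off.** Twelve weeks hold 12 × 5 = 60, 12 × 4 = 48 or 12 × 3 = 36 sessions. The average frequency needed to reach each late visit within 12 weeks is:

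- Visit 5 (40 sessions): 40/12 = 3.33 per week
- Visit 6 (50 sessions): 50/12 = 4.17 per week
- Visit 7 at its 60-session timing: 60/12 = 5.00 per week

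**Step 4. What fits if Visit 8 must also fall within 12 weeks.** Treatment must stop by week 12 − 4 = 8, which allows at most 8 × 5 = 40, 8 × 4 = 32 or 8 × 3 = 24 sessions. Sixty sessions in 8 weeks would need 60/8 = 7.5 per week, outside the stated range.

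**Step 5. Day count.** Assume a fixed weekday pattern with the first session on the day of consent (day 0), so that 12 weeks end on day 84.

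| Pattern | Late visit that misses day 84 | Session 60 | Visit 8 (+28 days) |
|---|---|---|---|
| Mon–Fri (5) | none through session 60 | day 81 | day 109 (15.6 weeks) |
| Mon/Tue/Thu/Fri (4) | Visit 6, session 50: day 85 | day 102 | day 130 (18.6 weeks) |
| Mon/Wed/Fri (3) | Visit 5, session 40: day 91 | day 137 | day 165 (23.6 weeks) |

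The day count is slightly shorter than the weekly figures because it ends at the last session rather than at the end of that week. Some misses are small: Visit 6 at 4 per week is late by one day. At 5 per week the slack is 84 − 81 = 3 days.

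**The case against.** The strongest defence has two parts.

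**The 12 weeks may mean treatment only.** The paragraph after the visit schedule calls the end-of-treatment visit the last control visit and places the follow-up visits during therapy. Sixty sessions at the highest frequency also take exactly 12 weeks. On this reading Visit 8 lies outside the period by design. The reading is plausible but not established, since the period starts at consent and nothing excludes Visit 8. It also removes the conflict only at 5 per week; at 4 and 3 per week, treatment alone overruns by 3 and 8 weeks.

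**All the figures are ceilings.** Sixty sessions, three cycles and 12 weeks are each stated as a maximum. If whichever ceiling is reached first governs, 36 to 60 sessions fit into 12 weeks and the treatment limits do not contradict each other. The provision for an earlier end-of-treatment visit is broad enough to allow this. But the protocol does not say that week 12 ends treatment. Even if it did, Visit 8 would fall after week 12 for anyone treated past about week 8.

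Two smaller points stand. The one-day miss in the day count rests on an assumed weekday pattern and on consent and first session falling on the same day, so the weekly figures should carry the argument. The consequence is also limited: the protocol ties no visit to week 12, and the end-of-treatment visit is brought forward rather than lost.

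**Conclusion.** The concern holds. On no reading do 60 sessions at 3 or 4 per week fit into 12 weeks, and Visit 8 after a full course falls outside 12 weeks at every permitted frequency. The excess is 4, 7 or 12 weeks at 5, 4 or 3 per week if Visit 8 belongs to the observation period, and 0, 3 or 8 weeks if it does not. The weekly figures assume a constant frequency, no missed sessions and no gap after consent; relaxing any of the last two makes the excess larger.

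Early clearance or termination shortens individual courses but does not turn 12 weeks into an upper bound for a patient who receives all 60 sessions. This should be fixed: the stated duration is wrong or incomplete as written, and how it is applied decides which late assessments take place. It does not by itself undermine the study.

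**What to change.** Reconcile three elements: the 12-week maximum, the 60 sessions at 3 to 5 per week, and the timing of Visit 8. Specifically:

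1. State the maximum treatment period and the post-treatment follow-up as separate durations, each with a defined starting point (consent or first session), so that every listed visit has a place within the stated study period.
2. Say whether reaching week 12 ends treatment. If it does, add this to the listed reasons for an earlier end-of-treatment visit, and say that session-count visits not reached by then do not take place.

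Which element changes is for the sponsor to decide. If only the stated duration and schedule text change, the cost is a wording correction with no extra patients, visits or measurements. A change to the frequency, the session maximum or the follow-up would go beyond wording.

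### The DLQI is the only quality-of-life questionnaire named, although patients from about 8 years are eligible; the instrument should be named by age band

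*Protocol*

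**What the plan says.** The Day 0 assessment list in the protocol contains a single quality-of-life entry, "quality of life assessment – DLQI", for all patients. The next entry adds further instruments: "Additionally, appropriate scales will be used depending on the disease". These are PASI, PGA, IGA, SCORAD, EASI, a VAS and the 10-item Pruritus Severity Scale, allotted by diagnosis. None is presented as a quality-of-life measure, and none is allotted by age.

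Item 2 of the inclusion criteria is "Age over 8 years of age" and item 2 of the exclusion criteria is "Age under 8 years of age". Neither list sets an upper age limit.

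The entry for Visit 7 (end of treatment) says that "we will re-evaluate the condition of the skin, quality of life, safety of the device used". The paragraph after the visit list adds that at this visit "the same parameters will be assessed as during the first one".

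**The concern.** The protocol ties one questionnaire to an age range that runs from school age through adulthood. If that questionnaire was written for adults, some of its items will not fit a child's life. Such items may be answered as no impact or left blank. Either way the score would say less about the child's burden, and less about any improvement between Day 0 and end of treatment, than the same score says for an adult.

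What is at stake is how the quality-of-life result can be read in the youngest eligible patients. This is a data-collection matter. A statistical analysis plan can decide how to tabulate scores, but it cannot recover a children's questionnaire that was never given.

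**Working it through.** The protocol gives no sample size, age mix, DLQI variance, target change or DLQI threshold. There is no figure to reproduce and nothing to compute, so the check compares the protocol's statements with one another.

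1. **Which instrument?** The Day 0 list names the DLQI and no other quality-of-life measure. It mentions no child version, age cut-off, or proxy or assisted completion.
2. **For whom?** The entry stands in the common part of the list, before the disease-specific scales, so it applies to all four disease groups. The groups are defined by diagnosis, and the only tailoring of instruments is by diagnosis.
3. **At what ages?** The inclusion text says over 8 and the exclusion text says under 8. A patient aged exactly 8 is left unclear, hence "about 8" here without further precision. On either reading, children and adolescents are eligible.
4. **When?** Quality of life is named at Day 0 and again at Visit 7, and Visit 7 repeats the first visit's parameters. Read literally, the DLQI is both the baseline and the end measure at every age.
5. **Does another criterion narrow the age range in practice?** Inclusion item 6 asks for "A patient who is able to understand the information related to the experiment, meet the requirements contained in the protocol of the experiment". This concerns understanding the study and complying with it. It sets no age band for a questionnaire, and a child can meet it while some adult-life items still do not apply.
6. **Which patients are affected?** This step needs a figure that the document does not give, the lower age limit of the DLQI. It is assumed here to lie between 16 and 18 years:
   - with a limit of 16, the affected ages are about 8 to 15, and patients aged 16 and 17 are not affected;
   - with a limit of 18, the affected ages are about 8 to 17.
7. **How large is the effect?** It depends on the share of enrolled patients below the limit and on how many items do not apply to them. The document gives neither, so the effect may be anything from nil to material.

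Steps 1 to 5 rest on the protocol alone. Step 6 rests on the stated assumption.

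**The case against.** The strongest objection is that nothing in the protocol says the DLQI is meant for adults, what its items ask, or that a children's version exists. Without that premise, a DLQI entry and a lower age of about 8 do not contradict each other. This stands to the extent that the point must be conditional. It does not remove the point. The intended age range is a basic property of a named instrument, which the sponsor can settle by reading its instructions.

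A second objection is that the one-line entry may be shorthand and the children's form was intended. That is possible, but the protocol tailors the other scales explicitly by disease and says nothing comparable about age. A site following the text would give everyone the same form.

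A third objection is that the consequence is limited. This stands. The protocol does not designate quality of life as a primary or key outcome. Severity and itch have their own scales. Each patient is compared on the same form at both times, and adult results viewed alone are untouched.

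A reader might also infer more than the document supports:

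- *That scores of minors and adults cannot be pooled.* The protocol states no pooling plan and no group mean for quality of life, and a statistical analysis plan may deal with this. There is no stated analysis here to call wrong.
- *That all minors are affected.* With a limit of 16, patients aged 16 and 17 are not. The right description is patients below the questionnaire's lower age limit.
- *That the loss can be put as a percentage.* One might argue that if 1 or 2 of 10 equally weighted items did not apply, the reachable score would fall by 1/10 = 10% or 2/10 = 20%, and measurable change with it. The item counts are not in the document. The step to change also fails in general: a smaller maximum reduces observed change in proportion only if the change would have been spread evenly over all items. A child scoring well below the maximum may lose little or nothing.

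**Conclusion.** The point holds as a conditional one. The protocol fixes a single quality-of-life questionnaire for all patients without regard to age, while admitting patients from about 8 years, and repeats it at end of treatment. If the DLQI is an adult instrument with a lower limit between 16 and 18 years, quality of life in patients below that limit would be measured with items that may not apply to them.

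The document does not support the stronger statement that the result in these patients is invalid, and it allows no estimate of the size. The number of patients below the limit is unknown and may be zero. This is a cheap improvement to the choice of instrument. It does not challenge the trial's severity or itch results.

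**What to change.** - Check the DLQI's own instructions for its lower age limit and state that limit in the protocol.
- In the Day 0 list, name the quality-of-life instrument by age band: the DLQI from that limit upwards, and the children's version of the index below it.
- Keep each patient on the version used at Day 0 whenever quality of life is assessed later, so that a birthday during the study does not change the instrument.
- Report scores from the two versions separately, or combine them only by a method specified in advance.
- If younger patients have already completed the DLQI, list their scores apart from the adult result.

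The cost is one more short questionnaire and a separate summary for it, with no extra procedure. The downside is that the quality-of-life sample is split by age, so each estimate is slightly less precise.

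### Does the absence of scored scales at Visit 1 leave the study without a sound pre-treatment baseline?

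*Protocol*

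**What the plan says.** The Protocol's visit schedule opens with "Day 0 - screening and inclusion, during which the following will be assessed". The list under that item includes the DLQI, and then adds the disease scales: "Additionally, appropriate scales will be used depending on the disease". Item 2 reads, in full, "visit 1 – first full-body blue irradiation". It names no scale and gives no interval from Day 0.

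The next listed evaluation is "Visit 2 – evaluation of the effectiveness and safety after 10 sessions of blue light phototherapy, Blood sample collection". Visits 3 to 6 follow the same pattern without naming scales. At Visit 7 the team will "re-evaluate the condition of the skin, quality of life, safety of the device used", and Visit 8 is a clinical assessment 4 weeks after therapy stops.

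Two sentences in the paragraph after the schedule also bear on the point: "At the last control visit (end of treatment visit) the same parameters will be assessed as during the first one" and "Photographic documentation will be carried out at each visit". Day 0 is the only visit with a parameter list, so it is the natural reading of the visit to which end of treatment is compared.

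**The concern.** The title aim is effectiveness. The four groups are diagnoses, not treatment arms, and no control is described, so any estimate of effect rests on change from the pre-treatment score. In such a design the position of that score matters. If Day 0 and Visit 1 fall on different days, whatever happens between them enters the change attributed to the device. With a single scored occasion before the first irradiation, that part cannot be separated afterwards.

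The schedule invites the worry. Day 0 and Visit 1 are separate items, the gap between them is not stated, and Visit 1 is the only numbered visit whose own entry mentions no evaluation. An analysis plan can name a baseline, but it cannot create a score that was never collected.

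**Working it through.** The Protocol states no sample size, effect size or standard deviation for this point, so there is no figure to reproduce. The check is a reading of the schedule with some supporting arithmetic.

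**1. What is measured before treatment (schedule, item 1).** Disease scales plus DLQI:
- psoriasis: 4 + 1 = 5
- eczema: 3 + 1 = 4
- atopic dermatitis: 4 + 1 = 5
- chronic pruritus: 2 + 1 = 3

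Every instrument has one score before the first irradiation, and the end-of-treatment visit repeats the set. A pre-post comparison is therefore possible on all of them. Visit 1 also has a photograph under the each-visit rule. That is a record of visible lesions, though not a score.

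**2. What the gap can contribute.** For any later visit:

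change from Day 0 = (Day 0 to Visit 1) + (Visit 1 to later visit)

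The first term is zero if both visits fall on one day, which the text allows. If they differ, the term is unobserved, and the document gives neither its size nor its direction.

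**3. Whether the plan builds in a drift.** Three features would make the first term systematically non-zero:
- *A score threshold for entry*, which brings regression to the mean. The inclusion criteria ask for a diagnosis, or for itch lasting more than 6 weeks; there is no severity cut-off.
- *A washout of previous treatment* between scoring and first exposure. None is described.
- *A separate screening window.* None is described: screening and inclusion are one step, and no listed criterion sets a laboratory threshold that would have to be awaited.

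**4. What the document says about the length of the gap.** The only relevant limit is the maximum of 12 weeks from consent, that is 12 × 7 = 84 days. Counting weekday sessions from first to last:
- 60 sessions at 5 a week: 11 × 7 + 4 = 81 days, leaving 84 − 81 = 3.
- 20 sessions at 5 a week: 3 × 7 + 4 = 25 days, leaving 59.
- 20 sessions at 3 a week: 6 × 7 + 2 = 44 days, leaving 40.
- If the 28 days to Visit 8 must also fit, the last two become 59 − 28 = 31 and 40 − 28 = 12.
- 60 sessions at 4 or 3 a week take 60/4 = 15 or 60/3 = 20 weeks, which already exceeds the limit.

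So the limit implies a very short gap for the fastest full course but is not a dependable bound in general.

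**5. Illustration of what a shift could do, on assumed values only.** Suppose there is no treatment effect and an untreated shift of g standard deviations (of the change score) before Visit 1. A two-sided 5% one-sample z-test with n patients then rejects with probability

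1 − Φ(1.96 − g√n) + Φ(−1.96 − g√n)

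For g = 0.2 and n = 20, g√n = 0.894 and the result is 0.145. Over g from 0.1 to 0.5 and n from 10 to 30 the range is 0.06 to 0.78; at g = 0 it is 0.05. Neither g nor n comes from the Protocol. The range shows only that the answer depends wholly on an unknown shift.

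**The case for a change.** The strongest argument for acting is that the remedy is cheap and cannot be applied later: 3 to 5 instruments at a visit that already takes place, and only when the days differ. Photographs do not replace those scores. In all four groups at least the 10-item Pruritus Severity Scale and the DLQI cannot be read from a photograph, and in chronic pruritus no listed instrument can. The lack of a control makes a clean baseline more valuable, and with one pre-treatment score the study could not demonstrate that the early shift was zero.

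Much of this is factually right. The interval is not stated, no scale is listed at Visit 1, and a score not taken cannot be recovered. What does not follow is that the plan is wrong. The argument needs a gap between the visits and a shift within it, and the document establishes neither. The gain is also limited: one repeat score over an unset and possibly very short interval says little about the untreated course of disease during the treatment weeks. Change after Visit 1, including any from the permitted emollients, and the absence of a control would remain as they are.

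**Conclusion.** The concern does not hold. The schedule supplies one full pre-treatment score on every listed instrument, at a combined screening-and-inclusion step, and repeats the set at end of treatment. No figure is wrong and no passages conflict on this point. The possible bias cannot be sized from the document: it is zero if the two visits share a day, and unknown in size and direction otherwise.

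This rests on reading the reference visit as Day 0 and on the absence from the Protocol of any severity cut-off, washout or separate screening window. It does not rest on the 12-week limit, which leaves about 3 days for a full course at 5 sessions a week but 40 to 59 days after a 20-session course (12 to 31 if Visit 8 is counted). The unstated interval and the unnamed baseline are details that an analysis plan, not available here, commonly settles. Scoring again at Visit 1 would be a reasonable preference, but its absence is not a defect.

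### The 12-week observation limit cannot hold 60 sessions at 3 to 5 per week plus Visit 8, and a Visit 7 result is status at each patient's own end of treatment, not at 60 sessions

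*Protocol*

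**What the plan says.** The opening list of the protocol allows at most 60 irradiations, given "to each side of the body of the patient (30 minutes in total), 3-5 times per week". The same list says that after consent "the observation period will begin and will last a maximum of 12 weeks".

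The visit schedule evaluates effectiveness after 10, 20, 30, 40 and 50 sessions (Visits 2 to 6) and places Visit 7, the end-of-treatment visit, after 60. Item 8 of the schedule then lets Visit 7 move for two reasons. One is early termination for any reason. The other is clearing: "if the skin lesions have completely disappeared before 60 irradiations - the end of treatment visit will take place earlier". The paragraph after the schedule repeats the clearing rule in different words: "In the case of remission of skin lesions earlier than envisaged in the study protocol, the end of treatment visit will take place earlier".

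That paragraph also makes Visit 7 the one visit tied to the Day 0 measurements: "At the last control visit (end of treatment visit) the same parameters will be assessed as during the first one". Item 9 times the last visit from the end of treatment: "Visit 8 – assessment of the clinical condition 4 weeks after the cessation of therapy".

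On the patients, the opening list says: "The study involves four groups of patients (patients with psoriasis, atopic dermatitis, eczema and chronic pruritus". For chronic pruritus, the disease scales listed at Day 0 are VAS and the 10-item pruritus scale.

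**The concern.** Two things are at stake.

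The first is the calendar. The observation limit, the session count, the weekly frequency and Visit 8 are all stated, and they do not fit together. Which of them gives way decides how many sessions and how many effectiveness checks a patient can have, and whether Visit 8 falls inside the study at all.

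The second is how a Visit 7 result may be read. The date of Visit 7 depends partly on the outcome (clearing) and partly on other events (early termination, possibly the 12-week limit). Visit 7 is the natural comparison with Day 0, so an end-of-treatment clearance rate could be taken for the rate after 60 sessions, which it is not.

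Two smaller matters affect the same visit. The trigger is complete disappearance in one place and remission in another. It also refers to skin lesions, and the protocol does not say what that means for patients whose listed disease scales measure itch.

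**Working it through.** **Inputs, all from the protocol:** at most 60 sessions; f = 3 to 5 sessions per week; observation of at most 12 weeks after consent; Visit 8 four weeks after treatment stops; scheduled checks at 10, 20, 30, 40, 50 and 60 sessions. The protocol states no clearance rate, sample size or effect size, so there is no figure to reproduce.

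**Step 1: the full course against the limit.** Weeks are counted from the first session, with none missed. The 12-week clock starts earlier, at consent, so this count favours the protocol.

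| f per week | Weeks for 60 sessions (60/f) | Visit 8, week (60/f + 4) | Sessions in 12 weeks (12 × f) | Scheduled checks reached |
|---|---|---|---|---|
| 3 | 20 | 24 | 36 | three (10, 20, 30) |
| 4 | 15 | 19 | 48 | four (10 to 40) |
| 5 | 12 | 16 | 60 | six (10 to 60) |

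Only the highest frequency reaches 60 sessions in 12 weeks. Even then Visit 8 falls four weeks outside the limit.

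**Step 2: if Visit 8 must also fall within 12 weeks.** Treatment can then last 12 − 4 = 8 weeks. That allows 8 × 3 = 24 sessions (two checks) to 8 × 5 = 40 sessions (four checks). Sixty sessions would need 60/8 = 7.5 per week, above the stated maximum of 5.

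**Step 3: how far the visits move.** A patient found clear at the 10-session check has Visit 7 at 10/5 = 2.0 to 10/3 = 3.3 weeks and Visit 8 at 6.0 to 7.3 weeks. A patient who completes 60 sessions has Visit 7 at 12 to 20 weeks and Visit 8 at 16 to 24 weeks. Visit 8 can thus fall anywhere from about week 6 to week 24. Clearing noticed between scheduled checks could bring it earlier still.

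**Step 4: direction of the difference.** Compare clearance recorded at Visit 7 with the clearance that would be seen if every patient were treated to 60 sessions and assessed then. Patients with the same status on both cancel, so

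Visit 7 rate − 60-session rate = A − B.

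- A is the share recorded clear at an early Visit 7 who would have relapsed by 60 sessions.
- B is the share recorded not clear at an early Visit 7 who would have been clear at 60 sessions. It arises from early termination, or from the 12-week limit if that ends treatment (at 36 sessions for a patient treated 3 times per week).

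A is zero if clearing lasts. B is zero if no uncleared patient stops before 60 sessions. The protocol gives no relapse rate and no early-stopping rate, so neither the sign nor the size of A − B can be found from it.

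**The case against.** **Both limits are maxima.** Nothing promises that every patient receives 60 sessions, and a patient treated 3 times per week might simply stop at 36. This stands as a possible reading, but it does not remove the conflict. The schedule puts Visit 7 after 60 sessions and moves it only for clearing or early termination, so reaching week 12 would have to count as early termination. Visit 8 would then still fall at week 16. Taking the observation period to mean treatment only would rescue 5 sessions per week, but not 3 or 4.

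**No 60-session rate is promised.** This stands. The protocol names no clearance endpoint, and endpoint definition and labelling are commonly left to the analysis plan, which is not at hand. Treating until clear, with follow-up timed from the end of treatment, is an ordinary design, and cumulative clearance is a legitimate quantity. The Visit 7 point is therefore conditional on a clearance rate being reported.

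**A stronger reading to resist.** A reader might infer that the early-visit rule must inflate the clearance rate, because it catches patients while clear. The documents do not support this. The same sentence brings Visit 7 forward for uncleared patients who stop early, and they pull the rate the other way (term B). Any numerical ratio would rest on assumed fluctuation, relapse and early-stopping rates, so none is offered.

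**A second one.** A reader might take Visit 8 to separate lasting from chance clearing. It cannot do so cleanly: patients are then off treatment, so a true responder who relapses after stopping looks the same as a patient who cleared by chance.

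**Conclusion.** The schedule conflict is firm and needs only arithmetic. The 12-week maximum cannot hold for any patient who completes 60 sessions, since Visit 8 then falls at 16 to 24 weeks. Within 12 weeks the stated frequencies give 36 to 60 sessions and three to six scheduled checks. The figures assume a constant weekly frequency and no missed sessions; missed sessions would widen the gap.

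The reading of Visit 7 follows from the visit rules: it is status at each patient's own end of treatment. This assumes that irradiation stops when the end-of-treatment visit is held, which the name of the visit implies but the text does not state outright. A clearance rate taken there could lie above or below a 60-session rate, or equal it, by an amount the protocol does not allow one to estimate. The protocol contains no mislabelled result; the point is a caution on how one should be presented.

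The two wordings of the trigger, and its meaning in chronic pruritus, are missing detail rather than error. Overall this is a point to consider, with medium confidence.

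**What to change.** 1. Reconcile the 12-week observation limit with the session count, the weekly frequency and the timing of Visit 8. Which of these governs is for the sponsor and investigators to decide. State whether the limit covers treatment only or includes Visit 8.
2. If a clearance rate at Visit 7 is reported, label it cumulative clearance by each patient's end of treatment (up to 60 sessions). Give the distribution of sessions received and the number of uncleared patients who stopped early. Show Visit 8 status beside it, noting that Visit 8 is off treatment and timed from each patient's own last session.
3. Reconcile complete disappearance with remission as the trigger for an early Visit 7, and state how the trigger applies in chronic pruritus.

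The treatment rule stays unchanged and no extra visit is asked for. The cost is protocol wording and a little extra tabulation. One check is needed on the way: Visits 2 to 6 and Visit 8 are described only in general terms, without named scales, so the protocol should confirm that clearing is recorded at Visit 8 in the same way as at Visit 7.
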